4.12 Subgroup Analysis

The primary endpoint and WOMAC C disability sub-scores will be analyzed using separate mixed model repeated measures for the following subgroups:

- Baseline WOMAC A pain score (\leq median, $>$ median)
- BMI ($<30 \text{ kg/m}^2$, $\geq 30 \text{ kg/m}^2$ and $< 35 \text{ kg/m}^2$, and $\geq 35 \text{ kg/m}^2$)
- Baseline Index Knee Pain (VAS: ≤ 74 , ≥ 75)

The median for the Baseline WOMAC A pain score will be calculated based on the FAS.

Change from Baseline to Week 12 in WOMAC A pain score will be summarized descriptively for the following groups:

- Age (≤ 65 years, > 65 years)
- Sex (Male, Female)
- Race (White, Non-White)
- Ethnicity (Hispanic or Latino, Not Hispanic or Latino)
- Site
- Region (US Sites, Denmark Sites, Hong Kong Site)

4.13 Plasma Concentration and Pharmacokinetic Analyses

Plasma DMPC and DPPC concentration data will be listed by individual subject and summarized by time and MM-II dose group. PK parameters of AUC, C_{\max} , C_{\min} , and T_{\max} will be summarized with descriptive statistics (n, mean, SD, geometric mean, coefficient of variation (CV), minimum, first, second (i.e., median) and third quartiles, and maximum). The PK Analysis Set will be used for the analysis. PK analysis will only be conducted at US sites.

AUC will be determined from the linear trapezoidal method using non-compartmental analysis. Pre-dose concentrations will be analyzed at time 0. All other concentrations will be analyzed using their actual time post-dose. Concentrations below the lower limit of quantification (LLOQ)

	CLR_17_17 Statistical Analysis Plan	
	Date: 30-Sep-2022	Page 22 of 28

occurring before the first quantifiable concentration will be analyzed as 0. Concentrations below the LLOQ occurring after the first quantifiable concentration will be considered missing. If a quantifiable concentration during the elimination phase occurs after an elimination phase concentration that is below the LLOQ, the concentration will be examined to determine if the concentration should be included in the calculation.

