ADAMTS	A disintegrin and metalloproteinase with thrombospondin motifs
AE	Adverse event
AESI	Adverse Event of Special Interest
ANCOVA	Analysis of covariance
ATC	Anatomical Therapeutic Chemical
AUC	Area under the concentration-time curve from time zero to time of last quantifiable concentration
BMI	Body mass index
C _{max}	Maximum observed concentration
COX II	Cyclooxygenase II
CS	Clinically significant
CTCAE	Common Terminology Criteria for Adverse Events
CTX	C-terminal crosslinking telopeptide of collagen
CV	Coefficient of variation
DMPC	Dimyristoylphosphatidylcholine
DPPC	Dipalmitoylphosphatidylcholine
ECG	Electrocardiogram
eCRF	Electronic case report form
EoS	End of Study
FAS	Full Analysis Set
huARGS	Aggrecanase degraded aggrecan
IA	Intra-articular
IP	Investigational product
LLOQ	Lower limit of quantification
MedDRA	Medical Dictionary for Regulatory Activities
MACE	Major adverse cardiovascular event
MMPs	Matrix metalloproteinases
MMRM	Mixed model repeated measures
NCS	Not clinically significant

	CLR_17_17 Statistical Analysis Plan	
	Date: 30-Sep-2022	Page 7 of 28

Abbreviation	Definition
NSAIDs	Non-steroidal anti-inflammatory drugs
OA	Osteoarthritis
PC	phosphatidylcholines
PK	pharmacokinetic
PN	Preferred name
PPAS	Per Protocol Analysis Set
PT	Preferred term
PtGA	Patient Global Assessment
SOC	System organ class
SD	Standard deviation
TEAE	Treatment emergent adverse event
T _{max}	Time to maximum observed concentration
VAS	Visual Analog Scale
WHO	World Health Organization
WOMAC	Western Ontario and McMaster Universities Osteoarthritis Index

	CLR_17_17 Statistical Analysis Plan	
	Date: 30-Sep-2022	Page 8 of 28

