Currently available medication regimens for most OA include non-opioid analgesics such as acetaminophen/paracetamol, nonsteroidal anti-inflammatory drugs (NSAIDs), and injectable hyaluronic acid. These pharmaceutical agents can provide transient pain relief quite effectively, but long-term use of NSAIDs has been found to be associated with increased risk of gastrointestinal bleeding, hypertension, cardiovascular events, congestive heart failure, and renal insufficiency, etc. Long-term opioid use for OA is generally discouraged due to lack of information on benefits as well as risks of addiction and other side effects. The NSAIDs in the form of topical application and cyclooxygenase II (COX II) inhibitors are considered somewhat safer than other NSAIDs in terms of gastrointestinal side effects, although COX II inhibitors are contraindicated in patients with a history of coronary artery disease. Because of the high incidence of side effects associated with long-term therapy of both nonselective and COX II selective NSAIDs, effective and safer alternative treatments for OA are urgently needed.

MM-II is composed of two surface active phospholipids

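### SAP 4.13 states no baseline adjustment for DMPC and DPPC, so any quantifiable pre-dose level would be counted in AUC, Cmax and Cmin as MM-II exposure (minor)

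*SAP*

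**What the plan says.** SAP 1.1 describes the product: "MM-II is composed of two surface active phospholipids". The analytes in SAP 4.13 are DMPC and DPPC, both phosphatidylcholines according to the abbreviation list.

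SAP 4.13 sets out the following:

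- **Display:** "Plasma DMPC and DPPC concentration data will be listed by individual subject and summarized by time and MM-II dose group".
- **Parameters:** AUC, Cmax, Cmin and Tmax, which "will be summarized with descriptive statistics (n, mean, SD, geometric mean, coefficient of variation (CV), minimum", followed by quartiles and maximum. No test is stated.
- **AUC:** "AUC will be determined from the linear trapezoidal method using non-compartmental analysis". The abbreviation list gives the span: "Area under the concentration-time curve from time zero to time of last quantifiable concentration".
- **Timing:** "Pre-dose concentrations will be analyzed at time 0", and "All other concentrations will be analyzed using their actual time post-dose".
- **LLOQ:** values below it are set to 0 before the first quantifiable value and treated as missing afterwards.

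No baseline-adjusted parameter appears. SAP 5.1 and 5.4 add only the use of actual and unscheduled sampling times, and SAP 6 lists no PK change. Section 4.13 carries no redaction marks. The definition of the PK Analysis Set in protocol 9.5.4 is cut off.

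**The concern.** The plan collects a pre-dose concentration but does not use it as a reference. It becomes a data point, and every later concentration enters as a total. Elsewhere SAP 5.1 defines the last pre-dose value as Baseline, and SAP 4.14.2 to 4.14.4 summarise changes from it for vital signs, laboratory values and ECG parameters. Section 4.13 does nothing comparable for plasma concentrations.

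A subject with a quantifiable pre-dose level therefore has that level integrated into AUC over the whole sampling span and added to Cmax. Cmin is affected too. In addition, 4.13 does not say whether the pre-dose sample may itself supply Cmax and Tmax.

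What is at stake is how exposure is read across 1, 3 and 6 mL in a trial meant to identify an optimal dose. Compressed ratios could make exposure look less than dose-proportional when it is not. A non-zero AUC could be taken as systemic exposure that the injection did not cause.

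**Working it through.** The visible documents give no background level, LLOQ, sampling times or expected PK value. There is no plan figure to reproduce, and every quantity below is an assumption.

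**1. Inflation and dose ratio for AUC.** Scale the background AUC to 1 and assume a dose-proportional increment, with r = (1 mL increment in AUC)/(background AUC).

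- Uncorrected AUC: 1 + r at 1 mL and 1 + 6r at 6 mL.
- Apparent 6 mL to 1 mL ratio: (1 + 6r)/(1 + r), against a true 6.
- Difference: (1 + 6r) − (1 + r) = 5r, the same as without background.

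| r | Apparent ratio | Difference (units of background AUC) |
|---|---|---|
| 0.01 | 1.06/1.01 = 1.05 | 0.05 |
| 0.1 | 1.6/1.1 = 1.45 | 0.5 |
| 0.5 | 4/1.5 = 2.67 | 2.5 |
| 1 | 7/2 = 3.50 | 5 |
| 5 | 31/6 = 5.17 | 25 |

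The ratio is pulled towards 1, but the absolute difference is intact.

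**2. A full profile.** Assume first-order absorption and elimination (ka 0.5/h, ke 0.03/h), samples at 0, 1, 2, 4, 8, 24, 72 and 168 h, linear trapezoidal AUC, and a constant background b expressed as a multiple of the 1 mL peak increment.

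- Uncorrected over corrected Cmax at 1 mL: 1 + b.
- Apparent Cmax ratio: (6 + b)/(1 + b).

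| b | Cmax inflation | AUC inflation | 6:1 Cmax ratio | 6:1 AUC ratio |
|---|---|---|---|---|
| 0.1 | 1.10 | 1.37 | 5.55 | 4.66 |
| 0.5 | 1.50 | 2.83 | 4.33 | 2.77 |
| 1 | 2.00 | 4.65 | 3.50 | 2.08 |
| 5 | 6.00 | 19.26 | 1.83 | 1.26 |

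Subtracting the pre-dose value returns every inflation factor to 1 and every dose ratio to 6. Tmax is 8 h with and without subtraction.

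**3. Zero background.** A pre-dose value below the LLOQ is 0 under the plan's own rule. Subtracting 0 changes nothing.

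**4. The pre-dose sample as the maximum.** With no increment and k exchangeable samples including the pre-dose one, the pre-dose sample is the largest with probability 1/k: 25% for k = 4 and 12.5% for k = 8. Those subjects would have Tmax = 0. This is a limiting case; any real increment makes it rarer.

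**5. What subtraction does when there is no increment.** Assume independent normal within-subject noise with SD s.

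- Negative differences set to 0: the mean adjusted concentration is s/√π = 0.56s although true exposure is nil. With k = 8, mean adjusted Cmax is 1.42s, and it is exactly 0 in 12.5% of subjects.
- Negative differences kept: the mean adjusted concentration is 0, so adjusted AUC is unbiased. Mean adjusted Cmax is still about 1.35s for k = 8, because it is the maximum of seven noisy values.

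**The case against.** The strongest reply is that the premise is not documented. No visible text says that DMPC or DPPC is measurable in plasma without treatment, and 4.13 provides for early values below the LLOQ. A reader might infer that the PK tables are contaminated in fact. The documents do not support that; they support only the conditional statement.

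Four other stronger readings also fail:

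- **Placebo levels are being withheld.** Concentrations are indeed "summarized by time and MM-II dose group", but the PK Analysis Set definition is cut off and the SAP set definitions are partly redacted. If only MM-II subjects were sampled, nothing is left out.
- **The tables could not show exposure rising with dose.** Additive background compresses ratios, not differences. Arithmetic means are planned, so a rise would still be visible.
- **These parameters are the only view of exposure.** The summary by time and the subject listings also show it, and the time-0 row would reveal any background.
- **Tmax is biased by the missing correction.** Subtracting one value from every sample does not move Tmax. Whether the pre-dose sample is eligible as the maximum is a separate matter.

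It is also fair to object that subtraction with negatives set to 0 creates exposure where there is none, and produces zeros that break the planned geometric mean. The fix must avoid that. Finally, every concentration is listed, so adjusted values could be derived later.

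What remains is that 4.13 is a complete, unredacted specification. Followed as written, it counts any quantifiable pre-dose level as exposure.

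**Conclusion.** The point holds in conditional form and is minor. SAP 4.13 computes AUC, Cmax and Cmin on total concentrations and states no baseline adjustment. If pre-dose values are quantifiable, AUC and Cmax are overstated and dose ratios are pulled towards 1.

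The size cannot be fixed from the documents. It runs from nil, when all pre-dose values are below the LLOQ, to a true ratio of 6 reading as 1.05 at r = 0.01. These figures rest on a dose-proportional increment, a constant additive background and assumed values of r. Because the protocol's PK text is partly redacted, the finding is that SAP 4.13 states no adjustment, not that none exists anywhere.

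The PK analysis is descriptive and restricted to US sites. The primary comparison of Week 12 WOMAC A change is untouched.

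**What to change.** In SAP 4.13:

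1. When pre-dose values are quantifiable, report baseline-adjusted AUC and Cmax (each post-dose concentration minus the subject's own pre-dose value) beside the uncorrected values.
2. Do not set negative differences to 0 when computing adjusted AUC.
3. Summarise adjusted parameters by arithmetic mean and median, since geometric means are undefined for zero or negative values. Keep the geometric mean for the uncorrected parameters.
4. Take Cmax and Tmax from post-dose samples only.
5. Summarise placebo concentrations by time only if placebo subjects were sampled and assayed.

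The cost is a few sentences and some extra table columns, with no new samples or visits. The uncorrected results stay available, so no information is lost. There are two downsides: adjusted values are noisier when the increment is small, and adjusted Cmax stays biased upward as the maximum of noisy differences. A footnote to the table should say so.

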4.14 Safety Analyses

Safety will be assessed by adverse events, laboratory assessments, vital sign measurements, ECG data, index knee examination, and physical examination abnormalities using the Safety Analysis Set.

4.14.1 Adverse Events

An AE is defined as “any untoward medical occurrence in a subject, or clinical investigation subject administered a pharmaceutical product, and which does not necessarily have a causal relationship with this treatment. An AE can therefore be any unfavorable and unintended sign, symptom or disease temporally associated with the use of an investigation product, whether or not related to the investigational product”.

Any relevant observations made (including physical examination findings, clinically relevant abnormal vital signs, clinically relevant laboratory abnormalities, and clinically relevant ECG findings) prior to or after administration of the single dose of IP are to be recorded on the AE eCRF. An AE relating to a pre-existing condition will only be recorded if there is a worsening of the pre-existing condition during study conduct with regard to nature, severity or frequency. An event will be considered a treatment-emergent AE (TEAE) if the start or worsening of the event was on or after the administration of IP. Summaries of adverse events will be limited to TEAEs, but listings of all events will be provided. A serious adverse event is an event recorded as ‘Serious’ on the adverse event eCRF page. Adverse events will be classified by MedDRA SOC and PT.

The overall summary of TEAEs will include frequencies and percentages and will be presented for the following:

- Overview of adverse events;
- All adverse events by SOC and PT;
- Serious adverse events SOC and PT;
- Adverse events by SOC, PT, and severity;
- Adverse events related to study treatment by SOC and PT

	CLR_17_17 Statistical Analysis Plan	
	Date: 30-Sep-2022	Page 23 of 28

An adverse event will be considered related to study drug if the relationship is “possibly”, “probably”, or “certainly”. The severity of an adverse event will be rated by the investigator as “mild”, “moderate”, or “severe”. Subjects experiencing multiple instances of the same PT are only counted once within each SOC and PT combination. Subjects experiencing multiple instances of the same PT will only be counted once according to the highest severity during the treatment emergent period when summarizing severity.

Serious adverse events, if present, also will be listed using verbatim and SOC/PT. Should any serious adverse events occur during the study, the serious adverse events are displayed in a table and a narrative for each serious adverse event included in the study report.

Adverse Events of Special Interest (AESIs) will be summarized descriptively. AESI-related safety endpoints include:

- Percent of subjects with severe infections, defined as any infection meeting the regulatory definition of a SAE, or any infection requiring IV antibiotics whether or not reported as a serious event, as per the regulatory definition
- Percent of subjects with malignancies (excluding carcinoma in situ of the cervix)
- Percent of subjects with non-melanoma skin cancer
- Percent of subjects with melanoma skin cancer
- Percent of subjects with major adverse cardiovascular event (MACE)
- Percent of subjects with treatment-related hypersensitivity reactions (e.g. anaphylaxis, urticaria, angioedema, etc.)

All AEs will be presented in full in a comprehensive listing including subject number, treatment regimen, severity, seriousness, action taken, outcome, relationship to treatment, onset/stop and duration. Details of SAEs and AEs leading to withdrawal will be listed separately.

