8.2.2 Serious Adverse Event

A SAE is any untoward medical occurrence that, at any dose

- results in death
- is life-threatening
- requires in-subject hospitalization or prolongation of existing hospitalization*
- results in persistent or significant disability/incapacity
- is a congenital anomaly/birth defect
- important medical event: Important medical events that may not result in death, be life-threatening, or require hospitalization may be considered as SAEs when, based upon appropriate medical judgment, they may jeopardize the subject or may require medical or surgical intervention to prevent one of the outcomes listed above. Examples of such events include allergic bronchospasm requiring intensive treatment in an emergency room or at home, blood dyscrasias (e.g., neutropenia or anemia requiring blood transfusion, etc.), convulsions that do not result in hospitalization, or the development of treatment dependency or treatment abuse.

NOTE: The term "life-threatening" in the definition of "serious" refers to an event in which the subject was at risk of death at the time of the event; it does not refer to an event, which, hypothetically, might have caused death if it were more severe.

*A planned hospitalization for pre-existing condition, or a procedure required by the Clinical Investigation Plan, without a serious deterioration in health or if the hospitalization is clearly not associated with an AE (e.g., hospitalization due to social / logistic reason) are not to be considered as SAEs.

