8.4 Assessment of severity, outcome and expectedness of Adverse Events

The severity of an AE will be characterized as:

- Mild: AE which is easily tolerated
- Moderate: AE sufficiently discomforting to interfere with daily activity.
- Severe: AE, which prevents normal daily activities.
- Life-threatening: The subject is at risk of death due to the AE as it occurred. This does not refer to an event that hypothetically might have caused death if it were more severe.
- Death: Death related to AE

Event outcome is categorized as: fatal, resolved, resolved with sequelae, resolving, not resolved, or unknown.

Action taken with respect to study treatment due to an AE is categorized as: none, unknown, or not applicable.

Other actions taken are categorized as: none, specific therapy/medication, surgical medical procedure, or (Prolonged) hospitalization.

Assessment of Expectedness will be determined by the version of the IB effective at the time of onset of the adverse event

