6. DEVIATIONS FROM THE PROTOCOL

The protocol specifies that the primary endpoint analysis will be performed by first testing for an overall treatment effect prior to testing pairwise comparisons using Fisher’s LSD Test. Comparisons between MM-II doses and 3 mL placebo will instead be analyzed using a step-down Dunnett testing method.

The wording of the subgroup analysis was clarified from the protocol as the subgroups themselves are not covariates but rather ways to separately analyze different subsets of the total subject population of interest.

The summary of physical examinations was changed to include Abnormal CS and Abnormal NCS to better reflect the information provided by the eCRF.

The protocol specified summarizing treatment compliance but was deemed unnecessary since this is a single injection study.

The reference to “confirmed” when discussing MACE was removed since MACE events will not be adjudicated.

The definition of the FAS in the protocol required subjects to have at least one post-Baseline primary efficacy assessment. The definition of the FAS has been modified to no longer require subjects to have at least one post-Baseline primary efficacy assessment.

	CLR_17_17 Statistical Analysis Plan	
	Date: 30-Sep-2022	Page 28 of 28

The definition of the PPAS was modified to require a non-missing Week 12 primary efficacy assessment instead of any non-missing post-baseline assessment and to exclude subjects with other factors that could influence the validity of the data for the primary efficacy variable that are not major protocol deviations.

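### Does the three-grade severity scale in SAP 4.14.1 leave life-threatening and fatal adverse events without a place in the severity table?

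*SAP*

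**What the plan says.** Protocol 8.4 lists five severity levels. The third is "Severe: AE, which prevents normal daily activities". Above it stand "Life-threatening: The subject is at risk of death due to the AE as it occurred" and "Death: Death related to AE". The same section records event outcome in a separate field, which has its own fatal category.

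SAP 4.14.1 describes the rating with three levels: "The severity of an adverse event will be rated by the investigator as" mild, moderate or severe. It lists five summaries of treatment-emergent events, one of them by system organ class, preferred term and severity. In that table a subject with repeated instances of one preferred term "will only be counted once according to the highest severity during the treatment emergent period".

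The section also provides for:

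- a table of serious events by system organ class and preferred term;
- a separate listing of serious events and a narrative for each;
- a full listing: "All AEs will be presented in full in a comprehensive listing including subject number, treatment regimen, severity, seriousness", together with outcome and relationship to treatment.

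SAP Section 6 records departures from the protocol. One is a category change in another safety domain: "The summary of physical examinations was changed to include Abnormal CS and Abnormal NCS to better reflect the information provided by the eCRF". It has no entry on adverse event severity.

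**The concern.** Both documents describe the same investigator rating, and they give different scales. The protocol's definition of severe is about daily activities. It does not, by its own terms, take in an event that puts the subject at risk of death or kills them, so merging the top two grades into severe would be a choice that the SAP does not state.

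If five grades were collected, a literal reading of the SAP leaves two of them with no row in the severity table and no stated rank in the highest-severity rule. The full listing shows severity as recorded, so table and listing might not agree.

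The table also matters for interpretation. Protocol 4.2, under the primary safety objective, expects no more moderate to severe events on MM-II than on placebo, and this is the only visible planned summary explicitly by severity. A reader unable to tell where the gravest events were counted would have a weaker basis for judging that expectation. Since Section 6 logs a comparable change to physical examination categories, its silence here looks like an oversight.

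**Working it through.** The documents give no figure to reproduce, so the check compares the texts and then follows what each way of handling the grades would do to the table.

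**Counts.** Protocol 8.4 has 5 levels and SAP 4.14.1 has 3, so 5 − 3 = 2 levels (life-threatening and death) have no SAP counterpart. Of the five treatment-emergent summaries in SAP 4.14.1 (overview; all events; serious; by severity; related), 1 is explicitly by severity.

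**Is there a rank?** Protocol 8.4 lists its terms from mild up to death. If five grades are in the data, highest severity has one natural reading.

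**What happens under each possibility?**

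1. *Three grades collected.* Every event has a row. Events affected: 0.
2. *Five grades collected, no life-threatening or fatal treatment-emergent event.* The two top rows would be empty. Events affected: 0.
3. *Five grades collected, with such events.* For one preferred term in one arm, let *a*, *b*, *c*, *d*, *e* be the numbers of subjects whose highest grade is mild, moderate, severe, life-threatening and death.
   - Five rows: *a*, *b*, *c*, *d*, *e*. Moderate or worse = *b* + *c* + *d* + *e*; severe or worse = *c* + *d* + *e*.
   - Top grades merged into severe: *a*, *b*, (*c* + *d* + *e*). Moderate or worse = *b* + (*c* + *d* + *e*), the same; severe or worse = *c* + *d* + *e*, the same.
   - Only the split within the top group differs.

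**Could events be dropped unnoticed?** Each subject counts once per preferred term, in the severity table and in the all-events table alike. The severity rows for a term should therefore add up to that term's row in the all-events table: *a* + *b* + *c* + *d* + *e*, apart from any events with severity missing. Omitting the top grades would leave a shortfall of up to *d* + *e*, which a routine cross-check between the two tables would show.

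**Where else do these events appear?** Protocol 8.2.2 begins its definition with "A SAE is any untoward medical occurrence that, at any dose" and includes death and life-threatening events among the criteria. Its explanatory note on life-threatening has the same sense as the 8.4 grade: actual risk at the time, not a hypothetical one. An event graded at either top level should therefore be recorded as serious. It then enters the serious-event table, the separate listing and a narrative. The full listing shows severity, seriousness and outcome together, so each event can be traced whatever row it takes in the severity table.

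**Does anything depend on the split?** Protocol 4.2 states an expectation. The visible text attaches no test, threshold or decision rule to it.

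**The case for a change.** The best case for a change is that the contradiction is plain and cheap to remove. Two sentences describe one rating and cannot both be right. The visible SAP text on adverse events shows no redaction at this point. Merging is a choice, and a choice about safety data is better written down before unblinding than left to a programmer. If the case report form held only three grades, the SAP would instead contain an unrecorded departure from protocol 8.4. On this view one document needs a correction either way, at the price of one or two sentences.

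The difference in wording stands, and so does the absence of a visible mapping. The rest is weaker:

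- The missing category depends on what the case report form collected, which the documents do not show. The SAP speaks of how the investigator rates severity, not only of how the table is laid out. Its authors knew the form: they matched the physical examination categories to it and defined serious events by its field. That leans slightly towards three grades without proving it.
- Little can be read into the silence of Section 6. Most of the protocol's safety analysis text is not visible. If it already planned summaries on three grades, there was no analysis change to log.
- The wording of protocol 4.2 fits a three-level scale as well as a five-level one. A reading of it that left out life-threatening and fatal events would be perverse.
- The freedom left to the programmer is narrow. Separate rows and merged rows give the same cumulative counts, and omission would show up against the all-events table.

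**Conclusion.** The two sections do state different scales, but the plan needs no change. Two of the protocol's five grades lack a named counterpart in one descriptive table out of five. The number of events concerned cannot be estimated, because the documents give no expected rate. It is zero if three grades were collected or if no life-threatening or fatal treatment-emergent event occurs.

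Otherwise the only thing left open is whether the top grades appear as their own rows or within severe. That would ordinarily be settled in the table shells from the grades actually in the data. No efficacy result, error rate, analysis set or serious-event report depends on it, and the cumulative counts relevant to protocol 4.2 are the same both ways. Writing the mapping into the SAP would be tidier but would not alter any conclusion.

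This rests on three assumptions: life-threatening and fatal events are recorded as serious, as protocol 8.2.2 requires; analysts tabulate every grade collected; and the tables are cross-checked in the usual way. The case report form and the protocol's adverse event analysis text were not available, so which scale was collected remains unknown.
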